13 SIDE EFFECTS, VIGILANCE

The responsibilities of each stakeholder in terms of vigilance will be detailed in a document (Safety management Plan) validated by the sponsor.

The CRO (Axonal-Biostatem) will be in charge of collecting incidents related to the DM and tolerance incidents related to the DM to the study's vigilance correspondent (VIGIPHARM).

The Sponsor will be responsible for requesting additional information from the investigators, writing narratives, submitting reports of DM-related incidents and DM-related safety incidents to the investigators and the CPP, and reconciling data from the vigilance database and the clinical database.

The Sponsor will ensure that DM incidents and DM tolerance incidents are identified, that a database for reporting DM incidents and DM tolerance incidents is maintained, that DM incidents and DM tolerance incidents are reported to the appropriate authorities, and that vigilance reports are prepared.

13.1 DEFINITIONS

An adverse event (AE) is any undesirable medical event, unintended illness or injury, or adverse clinical sign (including abnormality, laboratory finding) in subjects, users, or others, whether or not related to the investigational medical treatment. This definition includes events related to the investigational medical device or comparator and events related to the procedures involved. For users or other individuals, this definition is limited to events related to the investigational medical device.

Adverse Device Effect (ADE): An adverse event related to the use of the medical device under investigation. This definition includes any adverse event resulting from inadequacies or inappropriateness in the instructions for use, deployment, implantation, installation and operation, or malfunction of the medical device under investigation. It includes any event resulting from an error in use or intentional misuse of the medical device under investigation

Serious Adverse Device Effect (SADE)

Is an adverse effect of the device resulting in one of the characteristic consequences of a serious adverse event described below

A Serious Adverse Event (SAE) is any AE that:

- Leads to death or
- Leads to serious deterioration of the subject's health condition, which has resulted in
 - endangerment of life, illness or injury or,
 - a permanent impairment of a body structure or function or,
 - hospitalization or prolongation of a hospitalization or,
 - medical or surgical intervention to prevent life-threatening disease, injury or permanent impairment of a body structure or function
- Causes fetal distress, fetal death, birth defect or congenital malformation.

Note: a planned hospitalization for a pre-existing condition, or a procedure required by the protocol, with no severity on the deterioration of the health condition, is not considered a serious adverse event.

Medical and scientific judgment should be used to decide whether other IS should also be considered serious, such as medically relevant events that may not be immediately life-

threatening, contribute to death, or result in hospitalization, but which may pose a potential danger to the patient or require intervention to prevent one of the consequences listed in the definition above

Unexpected adverse reaction: any adverse reaction whose nature, severity or course is not consistent with the information about the products, procedures and methods used in the research

Suspected Adverse Reactions: All AEs for which the investigator or sponsor believes that a causal relationship with the investigational component can reasonably be considered are considered suspected adverse reactions.

Suspected Serious Unexpected Adverse Reactions (SUSARs): A suspected serious unexpected adverse reaction is any noxious and undesired response to an investigational product, regardless of dose:

- That results in death, endangers the life of the person who is the subject of the research, requires hospitalization or prolongation of hospitalization, causes significant or permanent disability or incapacity, or results in a congenital anomaly or malformation;
- Whose nature, severity, frequency or course is inconsistent with information about the products, procedures and methods used in the research;
- For which the investigator or sponsor believes that a causal relationship with the investigational medical device can reasonably be expected.

New information: Any new information that may lead to a reassessment of the risk-benefit ratio of the research or the product under investigation, to changes in the use of the product, in the conduct of the research, or in the documentation of the research, or to the suspension or discontinuation or modification of the protocol of the research or similar research.

Intensity: The intensity of adverse events is assessed by the investigator using the following classification:

- Mild Grade 1: adverse event usually transient and without impact on normal activities;
- Moderate Grade 2: adverse event sufficiently troublesome to affect normal activities;
- Severe Grade 3: An adverse event that significantly alters the patient's normal course of activities, or is disabling or life-threatening.

Device failure

- Deficiency of the medical device related to its identity, quality, durability, reliability, safety or performance

Note: Device defects include malfunctions, operating errors, and improper labeling.

Any defects in the medical device related to its identity, quality, durability, reliability, safety, or performance should be documented throughout the clinical trial and properly managed by the sponsor.

Medical device defects that did not result in an adverse event, but could have resulted in a medical event

(a) if none of the appropriate steps had been taken,

(b) if the intervention had not been made, or

c) if the circumstances had been less fortunate,
should be reported as part of the study

Accountability: The investigator and Sponsor assess both the relationship of the adverse event (AE) to the device under investigation and the relationship of the AE to a protocol intervention

13.2 INVESTIGATOR'S RESPONSIBILITIES

13.2.1 Notification of adverse events (AEs)

Patients will be encouraged to report any DM-related incidents and DM-related tolerance incidents to the investigator.

At each assessment, the investigator will interview the patient to determine if any adverse events have occurred.

The physician will report in the eCRF all DM-related incidents and DM-related tolerance incidents observed or spontaneously reported by the patient throughout the study (as soon as the patient's signed consent to participate in the study is obtained).

AEs not related to the DM or not related to the procedure for implanting the DM will not be reported in the eCRF. However, physicians must report any adverse reaction suspected to be due to a drug or product by mail to the regional pharmacovigilance center (CRPV) on which they depend or on the website <http://solidarites-sante.gouv.fr/soins-et-maladies/signalement-sante-gouv-fr>.

DM-related incidents and DM-related tolerance incidents will be documented in detail in the observation book (eCRF). The following information should be filled in:

- Date and time of AR onset,
- Duration of AE (indicating the total duration of the AE or symptom or determining this duration from the start and end dates and times of the evolution),
- Intensity of AE (mild, moderate, severe),
- The causal relationship of the AR to the DM AND/OR to the procedure related to the DM,
- Any action taken with respect to the product under investigation and to address this AR,
- Evolution of the AR (e.g. complete resolution, persistence...),

The investigator should assess the intensity, severity and causality of all adverse events.

These should be followed up until the event is resolved.

Determination of duration:

If the total duration of the AR or symptom is not directly indicated, it will be calculated from its onset and end dates.

Intensity Assessment :

The investigator will specify the intensity of the AE according to the following classification: mild, moderate, severe taking into account the possible degrees of intensity of the event according to the following definitions:

Slight	
 ▪ Causes mild or transient discomfort, not requiring intervention or treatment. ▪ Does not limit or interfere with daily activities.
Moderate	
 ▪ Causes enough discomfort to limit or interfere with daily activities. ▪ May require treatment.
Severe	
 ▪ Causes significant symptoms that prevent normal daily activities. ▪ May require an invasive procedure.

Accountability / causal relationship with the study product and research:

The sponsor will rule on the causality of the event that occurred.

Related	Any clinical or biological event with a chronological and semiological relationship compatible with the occurrence of the AR.
Unbound	The AR is clearly related to other causes, such as the patient's clinical condition or concomitant therapy.

Appraisal of AR development:

The investigator will also inform the Sponsor of any new follow-up information.

The investigator will specify the course of the AR according to the following classification:

- Favorable evolution/healing,
- In the process of recovery,
- Persistence of AR,
- Resolution / healing with residual effects (to be specified),
- Death,
- Unknown evolution.

At the end of the study, a list of incidents related to the DM and non-serious incidents of tolerance related to the DM will be published.

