Data collected	
Inclusion visit (V1)
 
 Signature of informed consent Socio-demographic data Age of diabetes, type, start of insulin therapy HbA1c at time of current pump prescription Current pump model Patient satisfaction Type of insulin Last HbA1c measurement Glycemic parameters Number of major glycemic events (ADA definition) in the past month, in the past 6 months Randomization of the pump model 
First follow-up visit (V2): 4 weeks
 
 Local tolerance and any adverse events Time-stamped recording of blood glucose values and events, hypo- and hyperglycemia, insulin doses administered. Glycemic parameters Technical incidents with the device (catheter occlusion, alarms, detachment, pain, etc.) Patient satisfaction 
End of study visit (V3): 12 weeks
 
 Local tolerance and any adverse events Time-stamped recording of blood glucose values and events, hypo- and hyperglycemia, insulin doses administered. Glycemic parameters Technical incidents with the device (catheter occlusion, alarms, detachment, pain, etc.) Patient satisfaction 
An additional 1 month of testing for the Omnipod group = V4 visit at month 4 to assess their satisfaction after using the Medtrum pump.
 
 Local tolerance and any adverse events Time-stamped recording of blood glucose values and events, hypo- and hyperglycemia, insulin doses administered.

	
 ○ Glycemic parameters ○ Technical incidents with the device (catheter occlusion, alarms, detachment, pain, etc.) ○ Patient satisfaction
Vigilance management	
Expected complications of pump use in the study.
 
All events that occurred during the study: medical device incident, serious or non-serious adverse event, serious or non-serious adverse event related to insulin injection.

Risk assessment	
Each patient is already using an insulin pump at the time of inclusion in the study. The use of another pump model (CE marked and already used in other countries) does not present any additional potential risk.

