3.1.4 Possible adverse events related to the use of the device

Investigators should report any events that occur during the study (see Chapter 13).

Tolerance problems have already been reported with the patches of insulin sensors and pumps already on the market. These are essentially events of the type of local skin allergy at the location of the adhesive used to attach the pump.

Other side effects, the severity and appearance of which are not known at this time, may occur and will be reported during the study.

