10.2 SECONDARY ENDPOINTS

The secondary endpoints were:

❖ HbA1c:

- Value measured in the laboratory from a blood sample taken before the D0 visit and just before the 3-month visit

❖ Glucose Level Measurements

- Average Glucose Measurements over each period and over the entire study duration
- Minimum and maximum values
- Time in range expressed as a % (see ADA and International Consensus on Time in Range recommendations^{25,26})

These values are automatically calculated by the FreeStyle Libre software and will be reported by the investigator.

❖ Glycemic events

- Number of symptomatic and non-symptomatic hypoglycemic episodes during the evaluation period, broken down by severity level (see below)

- Number of symptomatic and non-symptomatic hyperglycemia events during the evaluation period, broken down by severity level (see below)

This information is derived from the FreeStyle Libre data and the data entered by the patient in the PDM.

The definition of hypoglycemia and hyperglycemia is the ADA consensus definition²⁵ :

Outcome	Definition
Hypoglycemia	Level 1: glucose <70 mg/dL (3.9 mmol/L) and glucose \geq 54 mg/dL (3.0 mmol/L) Level 2: glucose <54 mg/dL (3.0 mmol/L) Level 3: a severe event characterized by altered mental and/or physical status requiring assistance
Hyperglycemia	Level 1—elevated glucose: glucose >180 mg/dL (10 mmol/L) and glucose \leq 250 mg/dL (13.9 mmol/L) Level 2—very elevated glucose: glucose >250 mg/dL (13.9 mmol/L)
Time in range	Percentage of readings in the range of 70–180 mg/dL (3.9–10.0 mmol/L) per unit of time

❖ Device tolerance

- Local skin tolerance at the pump site (adhesive hold) and at the FreeStyle Libre blood glucose sensor site (adhesive hold).
- Any local or systemic safety issues should be reported during the study, including the additional one-month phase at the end of the study for patients in the "OmniPod" group

❖ Incidents with devices

- Any type of incident involving the operation of the medical devices used, particularly for pumps: removal, control problems, transmission difficulties, obstructions, leaks, etc.

❖ Patient satisfaction

- Self-questionnaire evaluating satisfaction with the use of the device (pump+PDM)
- Final question regarding patient preference between the Medtrum device and the Insulet device

❖ Insulin treatment

- The insulin treatment used should be documented
- Delivered insulin doses will be derived from the pump's data logging

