7.5 ANALYSIS OF TOLERANCE DURING THE STUDY

Analyses will be performed overall and by pump group on the **tolerance population**. Prior to any analysis, all DM-related incidents and DM-related tolerance will be coded by the MedDRA regulatory medical dictionary (version 20.0 or later).

The number of patients who had at least one tolerance problem will be described. The following criteria will be described for each period and by pump group:

- Irritation/itching (yes; no)
 - If yes, maximum intensity (low; moderate; intense)
- Redness (yes; no)
 - If yes, maximum intensity (low; moderate; intense)
- Other adverse events (yes; no)
 - All other events related to tolerance will be given in a listing.

A summary table (number and percentage of patients with AEs and number of events) by organ system class (OSG) and preferred term (PT) will be presented for the following categories of events by dissociating incidents and tolerance related to the medical device:

- According to the link (device AND procedure)
- According to the link (device OR procedure)
- Depending on the severity
- Depending on the actions taken (de-boosting)

A listing of individual data will be provided describing all the information collected via the eCRF concerning the AE (including duration, resolution, severity criteria, linkage, severity etc.)

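### Non-serious adverse events that the unblinded investigator judges unrelated never reach the eCRF, so part of the between-pump tolerance comparison rests on attribution

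*Protocol*

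**What the plan says.** **Entry rule.** Protocol 13.2.1 first says what goes in: "The physician will report in the eCRF all DM-related incidents and DM-related tolerance incidents observed or spontaneously reported by the patient". It then says what stays out: "AEs not related to the DM or not related to the procedure for implanting the DM will not be reported in the eCRF".

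**Who judges.** The same section says "The investigator should assess the intensity, severity and causality of all adverse events" and, further on, "The sponsor will rule on the causality of the event that occurred". Protocol 13.1 has both investigator and sponsor assess the relationship. It treats an event as a suspected reaction if either of them finds a causal link reasonable. The trial is open-label.

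**Wider scope elsewhere.** The summary, under Vigilance management, lists "All events that occurred during the study: medical device incident, serious or non-serious adverse event". Its Data collected entry includes adverse events at each follow-up visit with no relatedness limit. Protocol 3.3 wants every SAE reported, related or not. Protocol 13.2.2 opens with device-related serious events, then requires the SAE form for all SAEs irrespective of cause.

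**Analysis.** Protocol 11.2.4 plans a group comparison of the number of patients with at least one tolerance problem. SAP 4.4.3 codes this as AL_PBTOL_D, which is 1 if the patient reported irritation/itching, redness or a further adverse event. No relatedness condition is attached. Protocol 11.2.5 and SAP 7.5 plan SOC/PT tables of events linked to both device and procedure, and of events linked to either.

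**The concern.** Relatedness is usually a recorded attribute of an event. Here, for non-serious events, it is a condition for the event to be recorded. The person applying it knows the allocation. All patients enter the trial on Omnipod. One arm keeps its familiar pump and the other moves to one it has not used, so the same headache or skin complaint away from the site could be attributed differently in the two arms.

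If that happens, a tabulated difference between pumps can appear, or be hidden, with no true difference in events. Nobody could check afterwards, because the unattributed events would not be in the database. A reader of the SAP would also take AL_PBTOL_D to count every further adverse event, while the protocol supplies only the attributed ones. The Supervisory Committee's stopping criterion on adverse-event risk (Protocol 13.4) would draw on the same incomplete record for non-serious events.

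**Working it through.** The documents give no assumed adverse-event rate and no power for tolerance, so there is no figure to reproduce. The check is a comparison of sections, followed by an illustration with assumed rates.

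**1. What happens to each kind of event**

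| Event | Protocol 13.2.1 | Other text | Result |
|---|---|---|---|
| Non-serious, attributed to device | entered | consistent | recorded |
| Non-serious, judged unrelated | not entered | summary lists it | **conflict; lost** |
| Serious, attributed | entered | 13.2.2: form and eCRF vigilance pages | recorded |
| Serious, judged unrelated | not entered | 3.3 and 13.2.2: SAE form regardless of cause | captured by the form |
| Irritation/itching, redness | no specific rule | SAP 7.5: yes/no per period with intensity, no attribution condition | appears to escape the filter |

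**2. The literal wording of the exclusion.** It removes an event that lacks the device link *or* lacks the procedure link.

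| Device link | Procedure link | Literal reading | Probable intent (drop only if neither) |
|---|---|---|---|
| yes | yes | kept | kept |
| yes | no | dropped | kept |
| no | yes | dropped | kept |
| no | no | dropped | dropped |

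Taken literally, only the first row survives, and the either-link table would equal the both-links table. That also contradicts the preceding instruction in 13.2.1 to enter all device-related incidents. Under the probable intent the two tables do differ, but the either-link table is then simply everything recorded.

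**3. The sponsor's role.** Protocol 13.1 and 13.2.1 give the sponsor a say on causality. For a non-serious event never entered, no section describes how the sponsor would learn of it. The investigator's judgement of unrelated is in practice final. The Supervisory Committee (13.4) adjudicates SAEs only.

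**4. What DM covers.** In Protocol 11.2.4 and the SAP 7.4.1 code, DM is the pump-group factor, so it spans both pumps. In Protocol 13.1, adverse events include those tied to the comparator, but adverse device effects are confined to the device under investigation. A site that reads DM as the Medtrum pump alone could leave Omnipod-arm events unrecorded.

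**5. Illustration (assumed values).** Let a proportion p of patients in *each* arm have a non-serious adverse event, and let c1 and c2 be the probabilities that it is attributed and so recorded. Then:

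- recorded proportions are p × c1 and p × c2, and the spurious difference is p × (c1 − c2);
- with n = 50 per arm (100 included per SAP 5.1, split 1:1), the chance of nominal two-sided p < 0.05 is about Φ[(d − 1.96 × SE0) / SE1], where d is the absolute difference, SE0 the pooled and SE1 the unpooled standard error.

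Worked case, p = 40%, 90% versus 50%: recorded 36% and 20%, d = 0.16; SE0 = √(2 × 0.28 × 0.72 / 50) = 0.0898; SE1 = √[(0.36 × 0.64 + 0.20 × 0.80) / 50] = 0.0884; (0.16 − 0.176) / 0.0884 = −0.18, giving 43%.

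| True p, both arms | Attribution | Recorded | Spurious difference | Chance of p < 0.05 |
|---|---|---|---|---|
| any | 90% v 90% | equal | 0 points | nominal 5% |
| 20% | 90% v 70% | 18% v 14% | 4 points | 8% |
| 40% | 90% v 70% | 36% v 28% | 8 points | 13% |
| 60% | 90% v 70% | 54% v 42% | 12 points | 22% |
| 20% | 90% v 50% | 18% v 10% | 8 points | 21% |
| 40% | 90% v 50% | 36% v 20% | 16 points | 43% |
| 60% | 90% v 50% | 54% v 30% | 24 points | 69% |

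Swapping the arms reverses the sign. For AL_PBTOL_D the effect is diluted, since patients with irritation or redness count anyway. If a proportion q have one of these in each arm, independently of other events, the difference becomes p × (c1 − c2) × (1 − q), which is half as large at q = 50%.

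**The case against.** Several stronger readings are tempting, and the documents do not support them.

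- *Only device-related events are collected at all.* Not so: SAEs are to be reported on their own form whatever the cause, and three independent members adjudicate their attribution.
- *The whole tolerance comparison is filtered.* Two of the three components of AL_PBTOL_D, irritation/itching and redness, are structured items with no attribution condition.
- *The link tables are meaningless.* Under the probable intent they still separate events with both links from events with one. Both documents also say that it is device-related incidents and tolerance that will be coded, which agrees with 13.2.1.
- *Sections 3.1.4 and 10.2 flatly contradict the rule.* Section 3.1.4 sits under a heading about device-related events and defers to Chapter 13. The line in 10.2, "Any local or systemic safety issues should be reported during the study", is a bullet under device tolerance. The summary is the clearer conflict.

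The threshold in 13.2.1 also leans towards inclusion: an event counts as unrelated only when another cause is clear. That leaves less room for attribution to diverge between arms. SAP 7.5 describes tolerance by pump group and names no test, the stated secondary objectives are descriptive, and the primary endpoint is untouched.

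All of this stands and narrows the point. It does not remove the conflict with the summary, the faulty either/or wording, or the mismatch between 13.2.1 and the unrestricted third component of AL_PBTOL_D.

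**Conclusion.** The point holds in limited form. For non-serious events, an unblinded relatedness judgement controls entry to the eCRF. This conflicts with the summary and leaves the sponsor's causality role without material to act on. The exposure is the further-adverse-event component of AL_PBTOL_D, the non-serious part of the SOC/PT tables, and whatever portion of the comparison planned in Protocol 11.2.4 uses them.

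A reader might infer that the comparison is biased, perhaps against the new pump. The documents do not show that. Bias needs attribution to differ by arm, and they give neither the extent nor the direction. The 0 to 24 point range rests wholly on assumed event proportions (20% to 60%) and attribution probabilities (50% to 90%). With equal attribution the only effect is under-counting. This is a worthwhile, inexpensive improvement to a secondary safety comparison and does not threaten the trial's main conclusion.

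**What to change.** **If events can still be recorded.** Reconcile Protocol 13.2.1 with the summary, 3.3 and 13.2.2:

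- enter every adverse event reported at visits, in both arms, with relatedness to device and relatedness to procedure as two separate fields;
- define DM so that it covers both pumps;
- in SAP 7.5, present all adverse events by pump group first, then related ones.

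The cost is modest extra data entry and a protocol wording change. Investigators already question patients about adverse events at each assessment, and the sample size does not change. Open-label reporting and attribution remain, but attribution becomes visible and can be set beside the full count.

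**If data collection is complete.** SAP 5.1 reports that inclusion has ended with 100 patients, and changing 13.2.1 would not by itself recover events never entered at earlier visits. Then state in SAP 7.5, and in SAP section 6 (currently marked as not applicable), that non-serious adverse-event results and the third component of AL_PBTOL_D cover investigator-attributed events only. Say how sites applied DM in the Omnipod arm and how the either/or exclusion was applied, and interpret between-pump differences in that light. This costs a few sentences.
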